### 4.2 Final Analysis

All final, planned analyses will be performed after the last participant has completed all study assessments, all relevant study data have been processed and integrated into the analysis database, and the database has been locked.

Any post-hoc, exploratory analyses completed to support planned study analysis, which were not identified in this SAP, will be documented and reported in appendices to the CSR. Any results from these unplanned analyses (post-hoc) will also be clearly identified in the text of the CSR.

## 5. SAMPLE SIZE DETERMINATION

The study is planned to enroll approximately 250 patients total in a 1:1 randomization, that is, 125 patients in each of the TNX-102 SL 5.6 mg and placebo arms. [REDACTED]

The interim analysis will re-evaluate these assumptions and the IDMC may recommend a sample size increase.

## 6. ANALYSIS POPULATIONS

The following analysis populations are planned for this study:

- **Safety Population (SAFETY):** All participants who receive at least 1 dose of study drug. Participants who are issued study drug, but return 100% of it (i.e., none consumed) will be excluded from the safety population; likewise, participants that have no follow up following receipt of study drug to indicate they took drug are excluded. All safety analyses and demographic/baseline characterization will be performed using this population, analyzed as treated; participants will be summarized under TNX-102 SL 5.6 mg if they were issued it at any visit.
- **Modified Intention-to-Treat Population (mITT):** All randomized participants who have at least a baseline and one post-baseline CAPS-5 assessment. This is the primary population for efficacy analyses and participants will be analyzed based on their randomized treatment.

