10.3. Visit 3 (Telephone Visit: Day 14)

Visit 3 will be done as a telephone call to the patient and should be conducted after 2 weeks of treatment, on Day 14 ± 3 days.

The following steps should be completed:

- Assess changes in concomitant medications
- Assess study drug compliance based on patient verbal report
- Assess occurrence of adverse events, including any oral adverse events and whether an unscheduled visit is indicated for an examination of the oral cavity
- Review patient instructions regarding drug dosing.
- Administer the ‘Since Last Visit’ C-SSRS

After all of the items have been reviewed with the patient, the patient should be given an appointment to return to the clinic for Visit 4, and be re-instructed, as necessary, on dosing instructions, and reminded to bring study medication back to the clinic at their next visit.

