A death occurring during the study, during the per-protocol follow-up period, or reported to the Investigator after study participation (no required post-study time limit) must be reported to Tonix or its designee(s) immediately, whether or not it is considered treatment-related. Initial SAE reports must be followed by detailed descriptions. These should include copies of hospital case records and other documents when requested. Telephone and e-mail reports must be confirmed promptly either by facsimile or by email. For reporting SAEs, one of Tonix's designated Medical Monitors should be called.

The Investigator or other study personnel must immediately inform the one of Tonix Medical Monitors by phone or email of any AE considered serious or otherwise significant, as described above. **In addition, a completed SAE report form must be submitted to [REDACTED]
[REDACTED] within 24 hours of initial awareness of the event.**

Contact information for the Medical Monitors is provided below:

For questions pertaining to the reporting of SAEs or the completion of SAE documentation, site personnel should call [REDACTED]

The investigator, or the sponsor or designee in the case of a central Institutional Review Board (IRB), also must notify the EC/IRB of the occurrence of the SAE, in writing, as soon as is practicable and in accordance with local law. A copy of this notification must be provided to Tonix or its designee.

In the event of an SAE that meets the criteria for expedited reporting, an Investigational New Drug (IND) Safety Report will be prepared for submission to the FDA.

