13.1. Populations for Analysis

The following populations will be defined for use in analyzing the efficacy and safety data in the study (see SAP for more details):

- Safety Population (SAFETY): All patients who receive at least 1 dose of study drug. All safety analyses and demographic/baseline characterization will be performed using this population, analyzed as treated, using the highest dose they were issued at any visit.
- Modified Intention-to-Treat Population (mITT): All randomized patients who have at least a baseline and one post-baseline CAPS-5 assessment. This is the primary population for efficacy analyses and patients will be analyzed based on their randomized treatment. See [Section 10.5.1](#) for early termination assessments.

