## 10. SAFETY AND TOLERABILITY ANALYSIS

The safety analysis will be run on the Safety population. The analysis of safety assessments in this study will include summaries of the following safety and tolerability data collected for each participant:

- Adverse Events
- Clinical Laboratory Investigations
- C-SSRS
- Vital Signs
- Visual Examinations of Oral Cavity
- Electrocardiogram (ECG) Parameters (Obtained at Screening only)
- Changes from baseline in participant-rated CSFQ-14
- MADRS

Summaries of continuous parameters will include raw values and change from baseline, as appropriate. Listings of safety data will also be presented.

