#### **10.1.2 Serious Adverse Events**

A summary of incidence rates (frequencies and percentages) of SAEs by treatment group, SOC, and preferred term will be prepared for the Safety population. A data listing of SAEs will also be provided, displaying details of the event(s) captured on the CRF.

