#### **10.1.3 Deaths**

A listing of deaths will also be provided for the Safety Population.

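### A death, or less often an SAE, in a participant whose dosing is never established can be missing from the planned death listing and the by-arm SAE table, because both are limited to a Safety Population that excludes such participants

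*SAP*

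**What the plan says.** Protocol 13.1 defines the population by intake: "Safety Population (SAFETY): All patients who receive at least 1 dose of study drug". It states no exclusion for missing follow-up and refers to the SAP for detail.

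SAP 6 repeats the one-dose definition and adds two exclusions. The first rests on a tablet count: "Participants who are issued study drug, but return 100% of it (i.e., none consumed) will be excluded from the safety population". The second rests on the absence of information: "likewise, participants that have no follow up following receipt of study drug to indicate they took drug are excluded".

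The outputs that depend on this population are:

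- SAP 10, all safety: "The safety analysis will be run on the Safety population".
- SAP 10.1.3: "A listing of deaths will also be provided for the Safety Population". No other death output is planned.
- SAP 10.1.2: the SAE incidence summary by treatment group, SOC and "preferred term will be prepared for the Safety population". The same section plans an SAE listing but names no population for it. SAP 10.1 says that the AE listings will show every AE.

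Reporting to the sponsor has no dosing condition. Protocol 12.3 covers "A death occurring during the study, during the per-protocol follow-up period, or reported to the Investigator after study participation", with no time limit after the study.

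**The concern.** The two exclusions in SAP 6 differ in kind. A full bottle count shows non-use. A lack of follow-up shows nothing about use, yet it leads to the same result. For most safety tables this matters little, because a participant with no contact after Visit 2 contributes no events. Deaths are different, since a relative, a hospital or a public record can report one without saying whether any tablet was taken.

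This is a PTSD trial that administers the C-SSRS at every visit, so a death by arm is something a reader of the safety report needs to see. If the plan is followed exactly, the sponsor could hold a death report that the only planned death listing omits.

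**Working it through.** The documents give no figure on this point, so there is nothing to reproduce. The check is to follow one participant through the text and then show the size on assumed counts.

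**Step 1: when dosing can become known.** Two bottles of 40 tablets (2 × 40 = 80) are dispensed at Visit 2 on Day 1 (Protocol 9.1). The first scheduled contact is a telephone call that "should be conducted after 2 weeks of treatment, on Day 14 ± 3 days", that is, Day 11 to Day 17. The first scheduled tablet return is Visit 4 on Day 28 ± 5, that is, Day 23 to Day 33 (Protocol 10.4). If a participant dies before the call, or is lost after Visit 2 and later reported dead, and the bottles never come back, there may be no record that a dose was taken.

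**Step 2: apply the rules to that participant.**

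| Output | Population stated | Is the death or SAE shown? |
|---|---|---|
| Death listing, SAP 10.1.3 | Safety Population | No |
| SAE incidence table by arm, SAP 10.1.2 | Safety Population | No |
| SAE listing, SAP 10.1.2 | None named | Unclear |
| AE listings, SAP 10.1 | None named; all AEs to be displayed | Unclear, given the general sentence in SAP 10 |
| Disposition, SAP 8.1 | Everyone in the database | Participant counted, but death is not a withdrawal category in SAP 7.1.3.1 |
| Report to sponsor, Protocol 12.3 | No restriction | Yes |

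**Step 3: illustrative size.** Take the planned 125 per arm. Assume that one participant in an arm has unconfirmed dosing and dies or has an SAE, and that there are no other such events in the arm.

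- Under SAP 6: 0/(125 − 1) = 0/124 = 0%. The exact 95% upper limit is 1 − 0.025^(1/124) = 2.9%.
- Counting all randomized: 1/125 = 0.8%, exact 95% CI 0.02% to 4.4% (lower limit 1 − 0.975^(1/125)).
- If five participants in the arm had unconfirmed dosing, one of them with the event: 0/120 under SAP 6, upper limit 1 − 0.025^(1/120) = 3.0%. The all-randomized result is again 1/125.

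The intervals overlap heavily. What changes is whether the event is visible at all.

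**The case against.** The strongest reply is that little is really lost. The event still has to be reported to the sponsor, and the participant stays in the disposition table. Before anyone is called lost to follow-up, SAP 7.1.3.1 requires three contact attempts, an approach to a close contact if one was named, and a certified letter. An SAE report is itself follow-up. Each AE record needs a causality assessment (Protocol 11.3.1) and an answer on whether onset preceded the first dose (SAP 7.3.1), and initial SAE reports must be followed by detailed descriptions. Most SAEs would therefore settle the dosing question. This stands, and it leaves death as the main route. It does not put the death into the listing.

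It can also be argued that the SAP rule is only the detail that Protocol 13.1 leaves to it, so that SAP 12 has no change to declare. That is reasonable, and the point does not depend on calling the rule an undeclared departure.

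A reader might infer more than the documents support:

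- *All SAEs are confined to the Safety Population.* Only the incidence table is expressly limited; the listings are ambiguous.
- *The first two weeks are the least observed.* Nominal contacts on Days 1, 14, 28, 56 and 84 give gaps of 13, 14, 28 and 28 days, so the first gap is the shortest.
- *The rule always under-reports.* For an AE seen in x confirmed dosers, x/124 is larger than x/125, so common AE rates rise slightly. The downward direction applies to the omitted deaths and SAEs.
- *Unreturned drug should count as exposure.* This sits uneasily with a definition based on at least one dose. SAP 11.2 sets a missing last dose to the day before the last attended clinic visit. With first dose on day D and Visit 2 the only visit, duration is (D − 1) − D + 1 = 0 days.

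**Conclusion.** The gap is real but narrow. Read literally, SAP 6 with SAP 10.1.2 and 10.1.3 allows a death after randomization, or less often an SAE, to be absent from the planned death listing and the by-arm SAE table when dosing was never established. The disposition table does not make this good, because it need not show a death as a death.

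The conclusion rests on two readings: that a third-party report silent on dosing does not count as follow-up indicating intake, and that the population named for each output will be applied as written. The probability is low. Estimating it would need the joint chance of no dosing evidence and a death or SAE, which the documents do not give, so 0/124 against 1/125 shows the form of the error and does not forecast it. The case for acting is that the omitted event would be of the most serious kind and the correction costs almost nothing.

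**What to change.** Amend SAP 10.1.2 and 10.1.3 so that all deaths and SAEs occurring after randomization are listed, and counted by arm, for all randomized participants. Add a flag for those with unconfirmed dosing, and state the population of the SAE listing explicitly. Keep the Safety Population and its denominators unchanged for all other AE tables.

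The cost is one extra listing or count and one derived flag. AE percentages are not diluted and the exposure rules in SAP 11.2 are untouched. The change should be made before unblinding.

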## 7. GENERAL ISSUES FOR STATISTICAL ANALYSIS

### 7.1 General Statistical Methodology

Descriptive summaries will be provided where appropriate for each of the primary and secondary variables. In general, tables will summarize data by treatment group and visit.

Baseline characteristic and safety tables will be completed for the Safety Population unless otherwise specified. Efficacy tables will be presented for the mITT Population.

Continuous, quantitative, variable summaries will include the number of participants (N) with non-missing values, mean, standard deviation (SD), median, minimum, and maximum.

Categorical, qualitative, variable summaries will include the frequency and percentage of participants who are in the particular category. In general, the denominator for the percentage calculation will be based upon the total number of participants in the study population for the treatment group unless otherwise specified.

Baseline values are defined as the last non-missing measurement prior to the first dose of study drug. Change from baseline will be defined as the post-baseline visit value minus the baseline value.

ET participants will only be followed if required to monitor an on-going adverse event or other condition.

Participants are not supposed to change study sites; however, should this be necessary to allow a participant to continue in the study, participants will be analyzed under the site where they were initially enrolled.

Study day after first dose is defined as assessment date – first dose date +1. Dates prior to first dose are defined as assessment date – first dose date.

All analyses will be performed using Statistical Analysis System (SAS®) Software version 9.4 or later.

Unless otherwise noted, 95% confidence intervals will be presented for statistical tests.

For the purposes of analyses that include a site covariate, sites that have two or fewer subjects will be pooled into a single site. If there are further problems with model convergence, other small sites causing issues will be included in this pooled site.

#### 7.1.1 Adjustments for Multiplicity and Other Alpha Control

##### 7.1.1.1 Multiplicity

To adjust for multiplicity and to control for overall type I error, a fixed sequence procedure will be applied to key secondary efficacy endpoints. If the primary analysis produces a result that is statistically significant at a given level, the key secondary endpoints will be tested in an ordered fashion at the same level. If the analysis for a secondary endpoint does not produce a statistically significant result, then the remaining secondary endpoint analyses will automatically be considered non-significant regardless of the p-value produced. In the case of an early stop or increase in sample size, the same

methodology/critical value used for the primary endpoint will be applied to the key secondary endpoints for the purposes of the sequential testing.

The order in which the key secondary endpoints, intended for labeling purposes, will be tested is as follows:

- i. Change from baseline in CGI-S score after 12 weeks of treatment (as a continuous outcome)
- ii. Change from baseline in the SDS total score after 12 weeks of treatment.
- iii. Change from baseline in the PROMIS Sleep Disturbance instrument T-score after 12 weeks of treatment

No other adjustments for multiplicity will be made and other p-values displayed in the output will be considered for descriptive summary purposes only and will not be used for formal inference. Additional details regarding statistical analysis for the listed endpoints can be found in [Section 9.2](#).

#### 7.1.1.2 Sample Size Increase

In the case of a sample size increase, the same inverse-normal method described in the primary efficacy analysis will be applied to the key secondary analyses to adjust the reported p-value; these will be tested at two-sided [REDACTED] to account for the sample size increase.

#### 7.1.2 Data Handling for Participants Who Discontinue Study Drug or Withdraw from the Study

Participants who withdraw/drop out from the study will have their ET visit data collected and included in the analysis based on the closest visit window (Week 4, 8 or 12). Visit windows will be assigned by splitting the periods between visits at the midpoint between the visits. If more than one record falls within the window, the one closest to the target date will be used in the analysis, with preference given to the scheduled visits in the case of equidistant visits.

#### 7.1.3 Procedures to Identify Reasons for Early Termination/Discontinuation

Reason for withdrawal will strongly contribute to the primary imputation algorithm; as such, the sites and sponsor will use the following categories and procedures to ensure that the withdrawal reason selected for the subject on the discontinuation case report form (CRF) page accurately represents the reason for withdrawal.

##### 7.1.3.1 Early Termination/Discontinuation Categories

The following categories for early termination/discontinuation are available to the sites:

**Insufficient Therapeutic Response (aka Lack of Efficacy or 'LOE')**: Patients who discontinue from the study due to the perception they are receiving little or no benefit from the Investigational Product (IP) and feel they must go on to some other option for therapy should be coded to Insufficient Therapeutic Response.

All patients are informed at the Screening Visit about the nature of double-blind, placebo-controlled clinical trials, including the fact that they may not receive any benefit from the

experimental treatment. It is emphasized that all information derived from their participation is important, whether or not they are experiencing improvement in their condition, and, via informed consent, they are agreeing to be compliant with the protocol for the 12 weeks regardless of symptom improvement. Therefore, in theory, LOE should rarely be utilized as a reason for discontinuing. However, occasionally real-world instances dictate that despite initially agreeing to complete all study visits and procedures, some patients feel they just cannot continue without some other therapeutic help and are therefore discontinued.

**Occurrence of an Adverse Event ('AE')**: Patients who discontinue from the study due to complaints of untoward medical events of a severity that interferes with their daily activities or causes much distress are coded to Occurrence of an AE. Patients who discontinue for this reason essentially are stating they would continue in the study if they were not experiencing the(se) adverse event(s).

**Lost to follow-up ('LTFU')**: Patients who miss study visits and are non-responsive to repeated phone calls, texts and/or emails requesting follow up should be coded to LTFU.

All patients are to receive at least 3 attempts at contact before the site sends a certified letter requesting the patient contact the site (and return study drug) before being deemed "Lost to Follow Up". Sites are to document in the source these 3 attempts made to contact the patient. Also, all sites are requested to ask patients at the Screening visit to provide the name and contact information of someone close to them whom the site may contact if they are having difficulty reaching the participant, to assist with successfully communicating with the participant. If the patient provided this information, this route is to be attempted before the certified letter. If the certified letter also fails to elicit a response from the participant, the site is expected to document the date the letter was sent, whether delivery and signature were confirmed, and that the patient is coded to LTFU.

**Investigator Decision**: Patients who are discontinued because the Principal Investigator (PI) thinks it is not in the best interest of the patient to continue study treatment should be coded to Investigator Decision. This category differs from AE in that there is not an identifiable treatment-emergent event that is driving this decision. An example would be if an investigator learns after randomization that the patient had not previously disclosed pre-existing medical condition that is contraindicated for inclusion, such as learning from medical records that do not arrive until after randomization that the patient has untreated or uncontrolled angle-closure glaucoma. This is a very rarely utilized reason for discontinuation.

**Withdrawal of consent by patient ('WOC')**: Patients who discontinue from the study due to not being able to continue with study visits because of life circumstances should be coded as discontinuing due to Withdrawal of Consent. The circumstances must be unrelated to perceived efficacy of the IP or to occurrence of AEs. Typical reasons in this category are the participant has to move out of range from the study site and return visits are no longer feasible, or the participant has had a life change, such as a new job, that does not allow time for study visits during available site hours. The burden is placed on the investigator to reasonably demonstrate that the discontinuation is not better accounted for by LOE or AE. Sponsor assessment of the appropriateness of WOC discontinuation

designation includes review of the participant's results efficacy measures, including CAPS-5 and PGIC, and recorded AE(s) occurring around the time of discontinuation. Any potential alternative explanation based on evidence of LOE or AE is presented to the investigator to challenge the categorization in WOC and encourage re-designation under LOE or AE if deemed more accurate and appropriate.

**Patient Non-Compliance:** Patients who are discontinued from the study due to not following study procedures, to a degree that they are impacting the integrity of the study, should be coded to Patient Non-Compliance. In most cases the patient has stopped taking their study drug.

Before choosing this option, the Investigator must determine that the non-compliance is not due to LOE or AE. This category should seldom be selected and should only be applied to real world instances where the patient is not following study procedures despite attempts at re-education by site staff.

Poor compliance with IP due to patient forgetting doses or other problems/circumstances that interfered with dosing would not be a reason to discontinue a participant. Rather, generally, all efforts are made to have patients with poor compliance remain in the study after re-education regarding daily dosing of IP and importance of not missing doses. Whereas outright refusal to comply with dosing by the patient would be considered a reason for discontinuation due to patient non-compliance after LOE and AE have been ruled out as primary causes of the non-compliance with dosing.

**Pregnancy:** Patients who become pregnant while in the study must be discontinued, with the reason for discontinuation coded to Pregnancy.

**Other:** Patients who discontinue for a reason that cannot be categorized under any of the above-mentioned categories should be coded to Other. Examples are the sponsor discontinued the study or the site can no longer participate in the study.

All other discontinuation reasons must be ruled out before "Other" can be selected.

